5. EFFICACY

All efficacy analyses will be based on the full analysis set.

The efficacy variables for this study are listed in Table 4.

Table 4: Efficacy Variables

Efficacy Variable		Endpoint
Time to all-cause discontinuation of study drug	
 Time to all-cause discontinuation of study drug 	Primary
MADRS	
 Change from baseline to Weeks 2, 4, 6, 12, 18, and 24 in the MADRS total score The proportion of subjects achieving (at Week 12) and sustaining remission at Weeks 18 and 24. Remission is defined as MADRS total score ≤ 12. The proportion of subjects achieving (at Week 12) and sustaining response at Weeks 18 and 24. Response is defined as $\geq 50\%$ improvement from baseline MADRS total score. 	Secondary Secondary Secondary

Efficacy Variable		Endpoint
	
 Change from baseline to Weeks 12, 18, and 24 in the MADRS total score in subjects with baseline ISI score ≥ 15 versus subjects with baseline ISI score < 15 	Secondary
	
 Change from baseline to Weeks 2, 4, 6, 12, 18, and 24 in the MADRS-6 total score 	Secondary
	
 Change from baseline to Weeks 2, 4, 6, 12, 18, and 24 in the MADRS-WOSI total score 	Exploratory
HAM-A	
 Change from baseline to Weeks 6, 12, 18, and 24 in the HAM-A total score 	Secondary
CGI-S	
 Change from baseline to Weeks 2, 4, 6, 12, 18 and 24 	Secondary
PGI-S	
 Change from baseline to Weeks 2, 3, 6, 12, 18 and 24 	Secondary
QLDS	
 Change from baseline to Weeks 2, 4, 6, 12, 18 and 24 	Secondary
PROMIS-SD	
 Change from baseline to Weeks 2, 6, 12, 18 and 24 	Secondary
PROMIS-SRI	
 Change from baseline to Weeks 2, 6, 12, 18 and 24 	Secondary
SMDDS	
 Change from baseline to Weeks 2, 4, 6, 12, 18 and 24 	Secondary
SDMT	
 Change from baseline to Weeks 6, 12, and 24 	Secondary
TMT-Part B	
 Change from baseline to Weeks 6, 12, and 24 	Secondary
HVLT-R	
 Change from baseline to Weeks 6, 12, and 24 	Secondary
CSD-M	
 Change from baseline in subjective sleep parameters after the first 6 weeks of treatment Change from baseline in subjective sleep parameters after 3 to 6 months of treatment (using the average of up to 7 morning measurements in Weeks 12, 18, and 24, respectively) 	Exploratory Exploratory

5.1. Analysis Specifications

5.1.1. Level of Significance

The primary efficacy endpoint will be evaluated at a two-sided significance level of 0.20. For all other efficacy endpoints, no multiplicity adjustment will be done and point estimates and confidence intervals will be presented.

5.1.2. Data Handling Rules

As sensitivity analyses, the change in MADRS total score and HAM-A total score will be analyzed using an analysis of covariance (ANCOVA) model, using last observation carried forward (LOCF) data. These analyses are further described in Sections 5.3.1.2 and 5.3.4.2.

For the analyses of remission of depressive symptoms based on MADRS total score (Section 5.3.2) and response of depressive symptoms based on MADRS total score (Section 5.3.3), subjects with missing values will be imputed as non-responders/non-remitters.

For the graphical presentations of the cumulative response rates, defined as the percentage of subjects experiencing at least a given value of percent reduction from baseline to Week 24 for MADRS total score (Section 5.3.3.2), both observed and LOCF data will be presented.

5.1.3. Imputation Methods for Missing Items

For MADRS, imputation of the total score when there are missing items is described in Section 5.3.1.1. Likewise, for PROMIS-SD and PROMIS-SRI, imputation of the total score when there are missing items is described in Sections 5.3.8.1 and 5.3.9.1, respectively. For QLDS, imputation of the total score when there are missing items is described in Section 5.3.7.1. For all other scales where multiple items are summed to create a total, if any item of the scale is missing at a visit, the total score for that scale at that visit will be left blank.

5.2. Primary Efficacy Endpoint

5.2.1. Definition

The primary efficacy endpoint, time to all-cause discontinuation of study drug, is defined as the number of days from the first dose of study drug to the last dose of study drug. Subjects who complete double-blind treatment are not considered to have discontinued.

5.2.2. Estimand

The primary estimand, the main clinical quantity of interest to be estimated in the study, is defined by the following 4 components:

Population: subjects with MDD who have had an inadequate response to current antidepressant therapy with an SSRI/SNRI, as defined through appropriate inclusion/exclusion criteria to reflect the targeted patient population;

Variable: time to all-cause discontinuation of study drug (see Section 5.2.1);

Intervention Effect: the effect of the initially randomized treatment together with the oral SSRI/SNRI antidepressant;

Summary Measure: the difference in survival distributions.

The primary analysis will be based on the full analysis set.

5.2.3. Analysis Methods

The primary efficacy endpoint, time to all-cause discontinuation of study drug, will be estimated by the Kaplan-Meier method and summarized (number of discontinuations, number of censored subjects, median, 25th and 75th percentile, if estimable) by treatment group.

A stratified log-rank test (stratified for baseline insomnia status) will be used to test the hypothesis that there is no difference between the JNJ-42847922 group and quetiapine XR in the probability of discontinuing study drug, using a two-sided 0.20 significance level.

As a sensitivity analysis, similar to the stratified log-rank test above, a log-rank test without adjusting for stratification factor will be carried out.

As an additional sensitivity analysis, the log-rank analysis may be repeated excluding PP site due to possible GCP issues.

The estimate of the hazard ratio and its 80% confidence interval will be provided based on the Cox proportional hazards model with treatment and baseline insomnia status as the factors. In addition, a similar model with treatment as the only factor will be carried out.

The distribution of the time to discontinuation of study agent will be displayed with Kaplan-Meier curves, for the full analysis set. Subjects who discontinued the double-blind phase at any time due to any reason will be considered an 'Event' and their date of last dose of study agent based on the exposure dataset will be used in the time to event calculation. Subjects who complete the double-blind phase will be censored and the date of last dose of study agent based on the exposure dataset will serve as the time of censoring. Kaplan-Meier curves will also be produced for the Week 12 timepoint (Day 84). Subjects who do not experience an event prior Week 12 will be censored at day 84.

In addition to time to all-cause discontinuation, the stratified log-rank analysis described above will be repeated for time to treatment-related discontinuation. Examples of potentially non-treatment related discontinuations include subjects relocating or traveling out of the area and unable to return for study visits.

5.2.3.1. Subgroup Analyses

Descriptive statistics (number of discontinuations, number of censored subjects, median, 25th and 75th percentile, if estimable) will be provided for the primary efficacy endpoint (time to all-cause discontinuation of study drug) by the subgroups identified in Section 2.6. Subgroup analysis will be performed using the Cox proportional hazards model. The model will include terms for treatment, subgroup and treatment-by-subgroup. One subgroup at a time will be included in the model. A forest plot with the corresponding hazard ratios and 80% CI will be presented for the subgroups. If there are insufficient numbers in the subgroups to draw meaningful conclusions, the subgroup analysis will not be performed. The Kaplan-Meier plots will be provided for the subgroups with baseline ISI ≥ 15 and baseline ISI < 15 .

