**Table 2: Dose Description**

Dose Level	Capsules
20-mg JNJ-42847922	20 mg and placebo
40-mg JNJ-42847922	20 mg and 20 mg
50-mg Quetiapine XR	50 mg and placebo
150-mg Quetiapine XR	150 mg and placebo
300-mg Quetiapine XR	150 mg and 150 mg

All subjects randomized to JNJ-42847922 will receive 20 mg as a starting dose. Subjects randomized to quetiapine XR will receive 50 mg once daily for 2 days, followed by an increase to 150 mg once daily on Day 3, as per prescribing guidelines in the product label. After the initial dosing period, dose adjustments may be made starting with the first scheduled clinic visit (Day 14). The first dose adjustment must be upwards. Subsequent adjustments may be made upwards or downwards within the study dose ranges (20 or 40 mg for subjects randomized to JNJ-42847922 or 150 or 300 mg for subjects randomized to quetiapine XR) if necessary, depending upon the investigator's assessment of the subject's clinical response and tolerability.

Adjustments of dose should only be made after a clinic visit (if needed may be an unscheduled visit) and assessment of efficacy and tolerability of the medication.

Subjects for whom tolerability at the lowest dose is either unacceptable or cannot be appropriately managed should be withdrawn from the study, and the AE recorded as a reason for discontinuation. For subjects on the highest doses, if there is a lack of response after a clinically appropriate treatment time, the investigator should consider discontinuing the subject due to lack of efficacy.

Subjects will administer the assigned study drug once daily at bedtime, approximately 3 hours after the last meal, from Day 1 to Day 167. Subjects are required to record the administration of study drug or any missed doses in subject diaries, which will be checked at each scheduled visit. The capsules must be swallowed whole and not chewed, divided, dissolved or crushed (see [Table 3](#)) for description of interventions.

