1.4. Sample Size Justification

The primary purpose of the study is to investigate potential differentiating features between JNJ-42847922 and quetiapine XR. Although the sample size was not chosen based on a specific

set of endpoints, for evaluating the time to discontinuation of study drug in the JNJ-42847922 group versus the quetiapine XR group, a one-sided log-rank test with an overall sample size of 100 subjects (50 in the JNJ-42847922 group and 50 in the quetiapine XR group) provides approximately 92% power at a 1-sided 0.10 significance level to detect a hazard ratio of 0.415, assuming the proportion of subjects who discontinue from study drug in the quetiapine XR group is 50%. The planned sample size of the study is consistent with the nature of a Phase 2 exploratory study.

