2.6. Definition of Subgroups

Subgroup	Definition
Baseline ISI score	
 • ≥ 15 • < 15 using the randomization stratification factor as entered into IWRS; this will also be used in the analyses as the baseline insomnia status
Baseline MADRS total score	
 • \leq median • $>$ median
MDD subtype based on SCID-CT	
 • With anxious distress • Without anxious distress based on the Structured Clinical Interview for Diagnostic and Statistical Manual of Mental Disorders-Fifth Edition (DSM-5) Axis I Disorders – Clinical Trials Version (SCID-CT)
Sex	
 • Male

Subgroup	Definition
	
 Female Undifferentiated
Age Group	
 18-34 35-54 55-64 65-70
Sex and Age Group	
 Adults (18-64) male, Elderly (≥ 65) male, Adults (18-64) female, Elderly (≥ 65) female
MDD with Anxiety based on HAMA-A	
 Yes, defined as baseline HAM-A total score ≥ 18 No, defined as baseline HAM-A total score < 18
Class of antidepressant study medication	
 SNRI SSRI
Final dose	
 Seltorexant 20mg Seltorexant 40mg Quetiapine XR 150mg Quetiapine XR 300mg
Number of antidepressants of sufficient dose and with inadequate response taken for at least 4 weeks during the current episode	
 1 2 or more based on the Massachusetts General Hospital-Antidepressant Treatment Response Questionnaire (MGH-ATRQ)
Number of major depressive episodes in lifetime, including current episode	
 ≤ 3 > 3
Prior medication use of adjunctive antipsychotics	
 Yes No
Prior medication use of benzodiazepines	
 Yes No
Baseline body mass index (BMI)	
 underweight $< 18.5 \text{ kg/m}^2$ normal $18.5 - < 25 \text{ kg/m}^2$ overweight $25 - < 30 \text{ kg/m}^2$ obese $\geq 30 \text{ kg/m}^2$
Race	
 categories as collected on eCRF
Ethnicity	
 categories as collected on eCRF

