4.4. Extent of Exposure

Total duration of exposure (including days off drug) is defined as (date of last dose of study agent – date of first dose of study agent) + 1. Number of doses is defined as the total number of dose administrations. Taking more than 2 tablets within 4 hours is considered as overdose.

Descriptive statistics (N, mean, SD, median, minimum, and maximum) for total duration of exposure (including days off drug) and for number of doses will be presented by treatment group for the safety analysis set.

The mode daily dose will be calculated for each subject, based on days on drug. The lowest mode dose is selected in case of ties. The frequency of mode daily dose will be presented by treatment group.

The mean daily dose of study agent for a subject is calculated as the sum of total daily dose during the treatment phase divided by the total number of days exposed. The final dose is the last non-zero dose received during the double-blind phase. The calculation of mean daily dose and final dose will exclude days off study drug. Descriptive statistics (N, mean, SD, median, minimum and maximum) for mean daily dose and final dose will be presented by treatment group.

A by-subject listing of study drug administration will be provided.

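### SAP 5.2.3.1 sends Final dose through a treatment-by-subgroup Cox model, but each of its four levels exists in one arm only, so it has no within-level hazard ratio to plot

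*SAP*

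**What the plan says.** SAP 5.2.3.1 first promises descriptive statistics of time to all-cause discontinuation by the Section 2.6 subgroups. It then specifies a Cox model fitted to one subgroup at a time: "The model will include terms for treatment, subgroup and treatment-by-subgroup". The output follows: "A forest plot with the corresponding hazard ratios and 80% CI will be presented for the subgroups". The only exit is a sentence about sample size: "If there are insufficient numbers in the subgroups to draw meaningful conclusions, the subgroup analysis will not be performed".

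SAP 2.6 lists Final dose among the subgroups. It has four levels, each naming one drug: two seltorexant doses (20 and 40 mg), quetiapine XR 150 mg, and "Quetiapine XR 300mg". Section 5.2.3.1 neither exempts Final dose, nor regroups its levels, nor gives it a different model.

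SAP 4.4 defines the variable: "The final dose is the last non-zero dose received during the double-blind phase". SAP 5.2.1 defines the primary endpoint as the "number of days from the first dose of study drug to the last dose of study drug". Protocol Section 6 gives the arms dose ranges that do not overlap, opens dose adjustment at the Day 14 clinic visit, and ties later adjustments to clinical response and tolerability.

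Elsewhere the SAP handles dose differently. Mode dose (5.3.1.2 for MADRS, 5.3.3.2 for time to sustained response) is only summarised, with no interaction model.

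**The concern.** A subgroup forest plot shows the treatment effect inside each subgroup level. That requires subjects from both arms at each level. For Final dose, knowing the level tells you the arm, so the comparison has nothing on its other side.

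Software that drops redundant columns may still print a number under the treatment label. That number would compare one seltorexant dose with one quetiapine dose, and the choice of reference level would decide which pair. On the plot it would stand beside genuine baseline subgroup effects.

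There is a second problem that recoding does not cure. Final dose is determined after randomisation, depends on how long the subject stays on drug, and is settled at the same last dose that ends the event time. Time to discontinuation by final dose therefore cannot be read as an effect of dose.

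**Working it through.** **The plan's own figure.** SAP 1.4 states about 92% power with 50 subjects per arm, hazard ratio 0.415, 50% discontinuation on quetiapine XR and one-sided alpha 0.10.

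- Expected events: 50 × 0.50 + 50 × (1 − 0.50^0.415) = 25.0 + 12.5 = 37.5.
- Schoenfeld: z = (√37.5 / 2) × |ln 0.415| − 1.282 = 2.693 − 1.282 = 1.411, giving 92.1%.

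The stated power reproduces, and this point does not touch it.

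**The cells of the Final dose model** (SAP 2.6 levels, Protocol Section 6 dose ranges):

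| Final dose level | Seltorexant arm | Quetiapine XR arm |
|---|---|---|
| Seltorexant 20 mg (S20) | possible | empty |
| Seltorexant 40 mg (S40) | possible | empty |
| Quetiapine XR 150 mg (Q150) | empty | possible |
| Quetiapine XR 300 mg (Q300) | empty | possible |

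**Algebra.** Let t = 1 for seltorexant and 0 for quetiapine. The log hazard relative to baseline is βt + γ_k + δ_k·t at level k, and the within-level hazard ratio is exp(β + δ_k). At a seltorexant level the data show only the sum β + γ_k + δ_k. At a quetiapine level they show only γ_k. So β + δ_k is never separated from γ_k at the first kind of level, and never appears at the second.

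**Rank.** There is 1 treatment column, 3 level columns and 3 products, 7 in all. Four non-empty cells, less the constant absorbed by the baseline hazard, give rank 3. A check on simulated data gave rank 3 at both n = 100 and n = 10,000.

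**Estimability.** A contrast is estimable if adding it to the design leaves the rank unchanged.

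| Model | Columns | Rank | Within-level treatment contrasts estimable |
|---|---|---|---|
| Final dose, 4 levels | 7 | 3 | 0 of 4 |
| Baseline ISI, 2 levels | 3 | 3 | 2 of 2 |
| Final dose recoded lower/higher | 3 | 3 | full rank |

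All 6 between-level pairs in the four-level model are estimable (3 are independent). They compare dose groups and are not subgroup treatment effects.

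**What a printed treatment coefficient would mean.** Assume the software keeps columns in order and drops each one that adds no rank, so that 3 are kept and 4 dropped:

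| Reference level | Treatment coefficient estimates |
|---|---|
| S20 | S20 vs Q300 |
| S40 | S40 vs Q300 |
| Q150 | S40 vs Q150 |
| Q300 | S40 vs Q300 |

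**Dependence on time on drug.** This is illustrative only. It uses the planning figures and an assumed constant hazard: ln 2 / 168 per day on quetiapine, and 0.415 times that on seltorexant. Subjects who stop before dose adjustment opens cannot be at the higher level. The expected number is 50 × (1 − exp(−hazard × d)); days 11 and 17 are the ends of the ±3-day visit window.

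| d (days) | Quetiapine XR (of 25 expected stops) | Seltorexant (of 12.5 expected stops) |
|---|---|---|
| 11 | 2.2 | 0.9 |
| 14 | 2.8 (11%) | 1.2 (9%) |
| 17 | 3.4 | 1.4 |

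These counts show that level and time on drug are linked by construction. They do not measure bias. The documents fix neither the size nor the direction of any distortion.

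**The case against.** The strongest reply is that the SAP already deals with this. If numbers are insufficient, the subgroup analysis will not be done, and one arm has zero subjects at every Final dose level. Applied that way, the sentence yields no entry, and only a wording improvement remains. That may well happen in practice. But the sentence speaks of numbers in the subgroups, and each dose level can be well populated while lying wholly in one arm. It does not clearly cover a gap that is known in advance and holds at any sample size.

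It can also be said that the link to Section 2.6 stands in the descriptive sentence, and that the Cox sentences do not name Final dose. That is true, but the natural reading is that they refer to the same subgroups, and nothing exempts this one.

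The relabelled coefficient rests on a software rule that no document specifies; a program that reports the within-level contrasts as missing would print nothing misleading. The point stands only as a conditional risk.

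Descriptive tables by dose are legitimate, and no passage presents the final-dose table as a dose comparison. That is accepted: the footnote is a precaution. A dosing error could put a subject in a cross cell, but that would not be a planned comparison.

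One further gap is real. A quetiapine subject who stops during the first two days has a last dose of 50 mg and fits none of the four levels.

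**Conclusion.** The concern holds. As written, SAP 5.2.3.1 calls for Final dose hazard ratios that cannot exist: rank 3 of 7, and 0 of 4 within-level treatment contrasts estimable. This follows from the level definitions and the separate dose ranges alone, and needs no assumption about sample size or hazards. A lower/higher recode would cure the rank but not the post-randomisation problem.

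The consequence is small. It reaches one forest-plot entry and the reading of one descriptive table in an exploratory subgroup analysis. No bias of any stated size or sign is claimed.

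**What to change.** Add a sentence to SAP 5.2.3.1 stating that Final dose is excluded from the Cox subgroup model and the forest plot. If the descriptive summary of time to discontinuation by final dose is kept, show it within each arm, with a footnote that final dose is determined after randomisation and that the table is not a dose comparison. The same edit should say how a subject whose last dose was 50 mg quetiapine XR is classified in that table.

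A landmark or time-varying-dose analysis within arm is optional and would still be confounded by response and tolerability.

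The cost is one sentence and one footnote, plus the classification rule. All that is lost is an entry that could not be produced as a subgroup treatment effect.

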5.3. Secondary Efficacy Endpoints

5.3.1. Change in Montgomery-Asberg Depression Rating Scale (MADRS) Total Score

5.3.1.1. Definition

A secondary efficacy endpoint is the change in MADRS total score from baseline to Weeks 12, 18, and 24. The MADRS will be performed by independent, centralized remote raters during the study. The MADRS is a clinician-administered scale designed to measure depression severity and consists of 10 items, each of which is scored from 0 (item not present or normal) to 6 (severe or continuous presence of the symptoms). The MADRS evaluates apparent sadness, reported sadness, inner tension, reduced sleep, reduced appetite, concentration difficulties, lassitude, inability to feel, pessimistic thoughts, and suicidal thoughts. The recall period for the MADRS is 7 days.

A total score (0 to 60) is calculated by adding the scores of all 10 items. Higher scores represent a more severe condition. Imputation of the total score will be performed only when 1 item score is missing. If 2 or more items are missing, the total score will be left missing. The total score will be imputed by calculating the sum of the scores of the non-missing items and multiplying it by the ratio of the maximum possible number of items (i.e., 10) to the number of non-missing items (i.e., 9).

The MADRS change from baseline at Week 24 is calculated as (MADRS total score at Week 24 – Baseline MADRS total score). Change from baseline to other time points is calculated similarly. Negative changes in MADRS total score indicate improvement.

5.3.1.2. Analysis Methods

Descriptive statistics of the actual values on Baseline, Week 2, Week 4, Week 6, Week 12, Week 18, Week 24, and at follow-up and the change from baseline to each postbaseline time point will be presented for MADRS total score by treatment group. A frequency distribution of the MADRS individual item scores at each time point will be provided by treatment group.

MMRM

A mixed model for repeated measures (MMRM) analysis of the observed data from the JNJ-42847922 and quetiapine XR groups will be used to adjust for important covariates. The MMRM will include time (scheduled Week), treatment (JNJ-42847922 and quetiapine XR), baseline insomnia status (present/absent), and treatment-by-time interaction as factors and baseline MADRS total score as a covariate. Data from the follow-up phase will not be used. An unstructured variance-covariance matrix will be used for observations clustered by subject. In case of convergence problems, alternative variance-covariance structures will be tried in the following order, with the first structure that converges being used in the analysis: heterogeneous Toeplitz, standard Toeplitz, and AR(1) with separate subject random effect. Subjects in the full analysis set who do not have complete data will still contribute to the estimates at each time point, but will have less weight in the analysis than those subjects with complete data. The

Kenward-Roger method will be used for approximating the denominator degrees of freedom. Based on the MMRM, the comparison between JNJ-42847922 and quetiapine XR will be performed using the appropriate contrasts directly from the MMRM analysis, using estimates at each postbaseline time point. A 80% confidence interval (CI) for the difference in least-squares (LS) means will be calculated based on the contrast test statistic.

As a secondary analysis, age and gender will be added to the MMRM model.

Means and mean changes from baseline (+/- SE) in MADRS will be presented graphically over time. Least squares mean changes from baseline (+/- SE) in MADRS will be presented graphically over time.

ANCOVA

As a sensitivity analysis, the change in MADRS total score from baseline to each postbaseline time point in the double-blind phase will be analyzed using an ANCOVA model, using LOCF and BOCF data. The ANCOVA model will include factors for treatment, baseline insomnia status (present/absent), and baseline MADRS total score as a continuous covariate. A 80% CI for the difference in LS Means will be calculated based on the contrast test statistic.

The last postbaseline observation during the double-blind phase will be carried forward as the “End Point (DB)” for that phase. Besides the end point assessment, the LOCF values will be created for intermediate postbaseline time points as well. These imputed time points will be labeled ‘WEEK X LOCF’.

For example, if a subject has a visit on Day 125 for the Week 18 visit and then a final visit on Day 130, the visit on Day 125 will be slotted to “Week 18” and “Week 18 LOCF” because Day 125 is closer to the target Day 126 than Day 130. The Day 130 visit will be used as “Week 24 LOCF” and “End Point (DB)”.

For subjects who discontinue treatment early, impute the missing MADRS scores post-discontinuation as the baseline value, and label as “Week xx BOCF” or “End Point (DB) BOCF”.

As a secondary analysis, age and gender will be added to the ANCOVA model.

SUBGROUP ANALYSIS

Baseline ISI Score

The ISI has 7 questions, each rated on a 5-point Likert scale ranging from 0 to 4. The total score is the sum of each individual item and can range from 0 to 28 (28 = most severe insomnia).

Subjects will be dichotomized based on their baseline ISI score (≥ 15 versus < 15) to evaluate whether there are differences in these subgroups (i.e., evaluating change from baseline to each postbaseline time point in the MADRS total score in subjects with ISI score ≥ 15 versus subjects

with ISI score <15). Descriptive statistics of the change from baseline to each postbaseline time point in the MADRS total score will be presented by treatment group for these subgroups.

Mode Dose

Descriptive statistics of the change from baseline to each postbaseline time point in the MADRS total score will be presented by treatment group and mode dose as defined in Section 4.4.

